9.4.4 Analysis of the Central Imaging Data

Imaging scans for a cohort may be read at the independent review facility when the minimum number of responders per investigator assessment (subjects with confirmed CR and PR) to claim promising antitumor activity at stage 1 are met based on the 2-stage BOP2 design. Central images may also be read in certain circumstances as determined by the sponsor.

Confirmed ORR, DOR, DCR, and PFS will be analyzed for the cohort with response assessment evaluated by BICR. These endpoints will be analyzed similarly as the corresponding endpoint per investigator assessment except that subjects are required to have measurable disease at baseline per BICR.

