12.9 RECIST Version 1.1

Table 1 – Time point response: patients with target (+/- non-target) disease.

Target lesions	Non-target lesions	New lesions	Overall response
CR	CR	No	CR
CR	Non-CR/non-PD	No	PR
CR	Not evaluated	No	PR
PR	Non-PD or not all evaluated	No	PR
SD	Non-PD or not all evaluated	No	SD
Not all evaluated	Non-PD	No	NE
PD	Any	Yes or No	PD
Any	PD	Yes or No	PD
Any	Any	Yes	PD

CR = complete response, PR = partial response, SD = stable disease, PD = progressive disease, and NE = inevaluable.

Table 2 – Time point response: patients with non-target disease only.

Non-target lesions	New lesions	Overall response
CR	No	CR
Non-CR/non-PD	No	Non-CR/non-PD ^a
Not all evaluated	No	NE
Unequivocal PD	Yes or No	PD
Any	Yes	PD

CR = complete response, PD = progressive disease, and NE = inevaluable.

^a a 'Non-CR/non-PD' is preferred over 'stable disease' for non-target disease since SD is increasingly used as endpoint for assessment of efficacy in some trials so to assign this category when no lesions can be measured is not advised.

Table 3 – Best overall response when confirmation of CR and PR required.		
Overall response First time point	Overall response Subsequent time point	BEST overall response
CR	CR	CR
CR	PR	SD, PD or PR ^a
CR	SD	SD provided minimum criteria for SD duration met, otherwise, PD
CR	PD	SD provided minimum criteria for SD duration met, otherwise, PD
CR	NE	SD provided minimum criteria for SD duration met, otherwise NE
PR	CR	PR
PR	PR	PR
PR	SD	SD
PR	PD	SD provided minimum criteria for SD duration met, otherwise, PD
PR	NE	SD provided minimum criteria for SD duration met, otherwise NE
NE	NE	NE

CR = complete response, PR = partial response, SD = stable disease, PD = progressive disease, and NE = inevaluable.

a If a CR is truly met at first time point, then any disease seen at a subsequent time point, even disease meeting PR criteria relative to baseline, makes the disease PD at that point (since disease must have reappeared after CR). Best response would depend on whether minimum duration for SD was met. However, sometimes 'CR' may be claimed when subsequent scans suggest small lesions were likely still present and in fact the patient had PR, not CR at the first time point. Under these circumstances, the original CR should be changed to PR and the best response is PR.

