4.1 Full Analysis Set

The full analysis set (FAS) consists of all enrolled subjects who receive any amount of study drug. The FAS will be used for primary analyses on overall survival (OS) and progression-free survival (PFS), as well as summaries for demographic, baseline characteristics and patient reported outcomes (PRO).

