5.2.3 Progression-free Survival per Investigator Assessment

PFS is defined as the time from the date of first dose of study drug to the date of first documented radiological disease progression (PD) per RECIST Version 1.1 by investigator assessment or death due to any cause, whichever comes first. PFS will be censored as the following:

- If a subject has neither PD nor death, PFS will be censored at the date of last evaluable radiological tumor assessment.
- If a subject starts a new anti-cancer treatment before any PD event or death, PFS will be censored at the date of last evaluable radiological tumor assessment prior to the date of new anti-cancer treatment.
- If a subject has PD or death immediately after two or more consecutive missed radiological tumor assessments, DOR will be censored at the last evaluable radiological tumor assessment prior to two or more missed radiological tumor assessments.
- If a subject does not have evaluable postbaseline radiological assessment, PFS will be censored at the first dose date of study drug.

For a subject who is censored, the last evaluable radiological tumor assessment refers to the subject's last radiological tumor assessment where the response is CR, PR or SD.

New anti-cancer treatment includes therapies captured on new anti-cancer therapy eCRF and new radiation/palliative radiation therapies captured on new radiation therapy eCRF that will impact target and/or non-target lesions.

PFS (in months) will be calculated as:

$$[(\text{Date of documented disease progression or death or censoring}) - (\text{Date of first dose of study drug}) + 1] / 30.4375$$

When a cutoff date is applied to PFS analysis, tumor assessment, death and new anti-cancer treatment occurring after the cutoff date will be excluded from the analysis.

The primary analysis population for PFS is FAS.

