5.3.2 Response Related Endpoints per RECIST Version 1.1 by Blinded Independent Central Review

Imaging scans for a cohort may be read at the independent review facility when the minimum number of responders per investigator assessment (subjects with confirmed CR or PR) at stage 1 are met based on the 2-stage BOP2 design. Central images may also be read in certain circumstances as determined by the sponsor. The following response related endpoints will be derived similarly as the corresponding endpoint per investigator assessment, except that timepoint tumor response per independent central review will be used.

- Confirmed ORR per BICR
- DOR per BICR
- DCR per BICR
- PFS per BICR
- BOR per BICR
- TTR per BICR

5.3.3 iRECIST Efficacy Endpoints by Investigator Assessment

For Cohort 9, additional endpoints of iBOR, iORR, iDCR, iPFS, and iDOR will be analyzed based on iRECIST guidelines.

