Death or documented iUPD right after two or more consecutive missed disease assessments	Date of last disease assessment prior to the missed visits	Censor
None of the above	Date of last disease assessment on study	Censor

iPFS = Date of Event or Censor – Date of First Dose +1

New anti-cancer therapy includes therapies captured on new anti-cancer therapy eCRF and new radiation therapy eCRF.

For a participant who is censored, the last evaluable radiological tumor assessment refers to the participant's last radiological tumor assessment where the response is not NE.

When a cutoff date is applied to iPFS analysis, tumor assessment, death and new anti-cancer treatment occurring after the cutoff date will be excluded from the analysis.

5.3.3.5 iDOR

iDOR is defined as the time from the date of first documented response (iCR or iPR that is subsequently confirmed) as assessed by investigator to the date of first documented radiological disease progression per iRECIST or death due to any cause whichever occurs

first. iDOR will only be calculated for subjects achieving a confirmed iCR or iPR. The same censoring rules as described in Table 1 for iPFS will be applied for iDOR.

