6.4.3.2 Endpoints per RECIST Version 1.1 by BICR

For cohorts with imaging scans read by BICR as defined in Section 5.3.2, confirmed ORR per BICR, DOR per BICR, DCR per BICR, PFS per BICR, BOR per BICR and TTR per BICR will be analyzed in the same way as the corresponding endpoints per investigator assessment as described in Sections 6.4.1 and 6.4.2.

Analyses based on RES population will require subjects to have measurable disease at baseline per BICR.

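### SAP and protocol define different populations for PFS per BICR; under the SAP's population, the CR/PR/SD censoring definition discards valid Non-CR/non-PD follow-up

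*SAP*

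**What the plan says.** **Population, SAP.** Section 5.2.3 states "The primary analysis population for PFS is FAS", and section 4.1 says that set "consists of all enrolled subjects who receive any amount of study drug", with no condition on measurable disease. Section 5.3.2 derives the BICR endpoints as their investigator counterparts, "except that timepoint tumor response per independent central review will be used". Section 6.4.3.2 then adds "Analyses based on RES population will require subjects to have measurable disease at baseline per BICR". That condition is tied to the RES, so it does not reach an endpoint analysed on the FAS.

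**Population, protocol.** Section 9.4.4 names confirmed ORR, DOR, DCR and PFS per BICR together and has them analysed like the investigator endpoints, "except that subjects are required to have measurable disease at baseline per BICR". Here PFS is included in the restriction.

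**Censoring definition.** SAP 5.2.3 censors a subject without PD or death at the last evaluable scan, and at first dose if there is no evaluable post-baseline scan. For a censored subject, the last evaluable scan is the "last radiological tumor assessment where the response is CR, PR or SD".

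**Response categories.** In Protocol 12.9, the table titled "Time point response: patients with non-target disease only" allows CR, Non-CR/non-PD, NE and PD. Its footnote advises against assigning SD when no lesion can be measured.

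**Contrast within the SAP.** For iPFS (5.3.3.4) the corresponding scan is the "last radiological tumor assessment where the response is not NE".

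**The concern.** The investigator and the central reader can disagree on whether baseline disease is measurable. Measurable disease is an entry criterion (Protocol 5.1), but both documents write a condition for the BICR analyses that would be pointless if disagreement never occurred. A subject with only non-target disease on central reading stays in PFS per BICR under the SAP, yet none of that subject's event-free scans carries a label the SAP accepts as evaluable, unless there is a CR. The event side of the rule works normally, so progressors and deaths are kept while event-free time is removed. The result is a Kaplan-Meier curve that is too low for a reason unrelated to the treatment or to the images.

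Separately, a programmer following the protocol and one following the SAP would use different denominators for the same table.

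**Working it through.** No sample size, power or event count is stated for PFS per BICR, so there is no planned figure to reproduce. The check traces the rule and then illustrates its size.

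**1. One record through the SAP rule.** Take central reads of Non-CR/non-PD at weeks 8, 16, 24 and 32, with the subject alive and without central PD at cutoff. No scan is CR, PR or SD, so no post-baseline scan is evaluable and PFS is censored at first dose.
- As written: (0 + 1) / 30.4375 = 0.033 months.
- With Non-CR/non-PD counted, censored at week 32 (day offset 224): (224 + 1) / 30.4375 = 7.39 months.
- Under Protocol 9.4.4: the subject is not in the analysis.

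**2. Who is affected.** The definition concerns censored subjects only. Follow-up is lost when a subject has no centrally measurable disease, has no central CR, and is censored. Censoring arises from having neither central PD nor death, from starting new therapy first, or from PD or death directly after two or more missed assessments. In cohorts 1 to 8, scheduled imaging stops once the investigator documents radiological progression (Protocol 7.1.1). A subject with investigator PD but no central PD can therefore also end up censored in the BICR analysis.

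**3. Size, by simulation.** From the documents: about 40 subjects per cohort, scans every 56 days (cohorts 1 to 8), and at least 6 months of potential follow-up at the primary analysis (SAP 6.8). Assumed, because the documents do not say:
- exponential PFS with true median 4 or 8 months;
- follow-up uniform over 6 to 18 months;
- 2% per month starting new therapy before central PD;
- share without centrally measurable disease of 5%, 10% or 20%, unrelated to prognosis, with no CR among them.

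Mean results over 4,000 cohorts per setting:

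| True median | Share | Subjects affected of 40 | 6-month PFS, scans counted | 6-month PFS, SAP as written | Difference (points) | 6-month PFS, subjects excluded |
|---|---|---|---|---|---|---|
| 4 mo | 5% | 0.50 | 0.386 | 0.380 | 0.6 | 0.386 |
| 4 mo | 10% | 0.99 | 0.384 | 0.371 | 1.3 | 0.384 |
| 4 mo | 20% | 1.97 | 0.384 | 0.359 | 2.5 | 0.385 |
| 8 mo | 5% | 0.93 | 0.619 | 0.611 | 0.8 | 0.619 |
| 8 mo | 10% | 1.85 | 0.620 | 0.603 | 1.7 | 0.621 |
| 8 mo | 20% | 3.68 | 0.621 | 0.586 | 3.5 | 0.621 |

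The last column is the protocol's population. It agrees with counting the scans to within 0.001.

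**4. Scale.** Ignoring censoring before 6 months, the standard error of a proportion of 0.62 with n = 40 is √(0.62 × 0.38 / 40) = 0.077, or 7.7 points. The largest shift in the table is 3.5 / 7.7 = 0.45 of a standard error.

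**The case against.** The strongest reply is that the protocol governs and the SAP describes itself as elaborating it. Protocol 9.4.4 removes these subjects from PFS per BICR, so the censoring problem never arises. This stands in part: a reader might infer that the plan definitely keeps these subjects, and the documents do not support that. But SAP 6.4.3.2 attaches the condition to RES analyses and assigns PFS to the FAS, so the conflict remains and the SAP reading has the fault.

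A reader might also infer that every subject without centrally measurable disease is censored on day 1. That is too broad. PD and death normally count as events, and a central CR is an evaluable scan.

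A third inference would be that a planned comparison of BICR with investigator PFS is distorted. Neither document plans such a comparison. The final judgement of promising activity may take central imaging data into account (Protocol 9.11, SAP 6.7), but no decision boundary uses PFS per BICR.

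Finally, it can be said that programmers would treat Non-CR/non-PD as SD in practice. Nothing in the SAP maps one to the other, and the footnote in Protocol 12.9 advises against it.

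The point that central reading is optional, and that the share affected may be small, stands in full.

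**Conclusion.** Two linked faults are established from the text: a protocol/SAP conflict on the population for PFS per BICR, and an evaluability definition in SAP 5.2.3 that omits a category the protocol's own response table produces. Under the SAP population the direction of the bias is downward, because only event-free time is lost.

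The size cannot be fixed from the documents. The range of 0.6 to 3.5 points in 6-month PFS depends on an assumed 5% to 20% disagreement on measurability and on the assumed PFS, follow-up and new-therapy rates. It is small against sampling error in a cohort of 40.

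The consequence is limited to an exploratory, descriptive endpoint in cohorts that are centrally read. Confirmed ORR by investigator, the interim and final responder boundaries, and BICR endpoints run on the RES are unaffected. This is a minor correction, worth making because it is cheap and removes an ambiguity.

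**What to change.** 1. In SAP 5.2.3, define the last evaluable assessment for a censored subject as one with a response of CR, PR, SD or Non-CR/Non-PD, that is, neither NE nor PD. This follows the approach taken for iPFS, although the iPFS text excludes only NE.
2. State one population for PFS per BICR, in the same terms, in SAP 6.4.3.2 and Protocol 9.4.4. Either choice is sound:
   - the FAS with the definition in step 1, limiting the condition in Protocol 9.4.4 to ORR, DOR and DCR; or
   - only subjects with measurable disease per BICR, adding PFS to the condition in SAP 6.4.3.2.

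The two choices gave nearly the same estimate in the simulation, so the essential step is to choose one and align the documents. The cost is one definition sentence and one derivation line, plus one phrase in whichever document moves. No data collection, imaging or sample size changes. If BICR results for any cohort have already been produced, the study report should say which population and definition were used.

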5.2.4 Overall Survival

OS is defined as the time from the date of first dose of study drug until the date of death due to any cause. For a subject who is not known to have died by the end of study follow-up, OS

is censored at the date of last known alive date or at the analysis cutoff date, whichever is earlier. All dates which can support a subject's survival status (i.e., lab testing date, drug administration date) will be used to derive the last known alive date. Subjects with death or last known alive date after the analysis cutoff date will be censored at the cutoff date.

OS (in months) will be calculated as:

$$[(\text{Date of death or censoring}) - (\text{Date of first dose of study drug}) + 1] / 30.4375$$

The primary analysis population for OS is FAS.

5.2.5 Derivation of Best Overall Response and Sum of Diameters

Best overall response and sum of diameters (SOD) will be derived per RECIST Version 1.1 for the purpose of analyzing response related endpoints, e.g., ORR, DOR, DCR.

5.2.5.1 Best Overall Response

BOR is determined based on all available timepoint tumor response data for a subject. Responses recorded after new anticancer therapy or PD will be excluded from BOR derivation.

BOR with Confirmation

Confirmation of CR or PR should occur at the subsequent assessment no less than 4 weeks following the initial assessment at which CR or PR is observed. BOR with confirmation will be derived according to below criteria per RECIST Version 1.1:

- If a subject has at least 2 CR and the first and the last CR dates are at least 28 days apart, then the BOR for this subject is confirmed CR.
- If a subject has PR and another CR/PR at least 28 days apart, then the BOR for this subject is confirmed PR.
- For those subjects who do not have confirmed CR or PR, if the subject has at least one tumor assessment record of CR/PR/SD which is at least 49 days after the first dose, then BOR is defined as SD.
- For subjects who do not have confirmed CR, confirmed PR, or SD, as defined above, but they have a tumor assessment of PD, their BOR is PD.
- Otherwise, BOR is defined as Not Evaluable (NE). For subjects without any postbaseline tumor assessment, BOR is defined as No Data (ND) which is a subcategory of NE.

BOR Regardless of Confirmation

The BOR regardless of confirmation for a subject is defined at the best timepoint tumor response in the order of CR, PR, SD, PD and NE. SD must be documented as present at least once at or after 49 days post first dose for BOR to be SD.

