Confirmed ORR per investigator assessment is the primary endpoint. Confirmed ORR is defined as the proportion of subjects whose objective response is confirmed CR or PR according to RECIST Version 1.1. Response (CR or PR) must be confirmed with a repeat imaging scan 4 weeks (28 days + 7-day window) after first response.

Blood samples for pharmacokinetics and ATA will be collected at protocol-specified time points. Validated assays will be used to measure the concentrations of enfortumab vedotin and MMAE in serum or plasma and to assess ATA. Samples for exploratory biomarkers will be collected at protocol-specified time points. Enfortumab vedotin biomarker assessments will not be used for subject selection.

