9.4.3 Analysis of Other Efficacy Endpoints

9.4.3.1 Best Overall Response

BOR will be determined based on all available tumor time point response data for the subject. Responses recorded after new anticancer therapy or progressive disease (PD), will be excluded from BOR derivation. A frequency table of BOR will be presented for each cohort and overall.

The BOR will be derived according to below criteria per RECIST Version 1.1:

- If a subject has at least 2 CR and the first and the last CR dates are more than 28 days apart, then the BOR is defined as confirmed CR.
- If a subject has PR and another CR/PR more than 28 days apart, then the BOR for this subject is confirmed PR.
- For those subjects who do not have confirmed CR or PR, if the subject has at least 1 tumor assessment record of CR/PR/SD which is at least 49 days after the date of the first dose, then BOR is defined as SD.
- For subjects who do not have confirmed CR, confirmed PR or SD defined as above, but they have the last tumor assessment as PD, their BOR is PD.
- Otherwise, BOR is defined as Not Evaluable (NE) or No Data (ND) for the subjects without any post-baseline tumor assessment data.

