5 SUMMARY OF ENDPOINTS

5.1 Primary Efficacy Endpoint

The primary efficacy endpoint for this study is confirmed ORR per RECIST Version 1.1 by investigator assessment.

Confirmed ORR is defined as the proportion of subjects whose best overall response (BOR) is a confirmed CR or confirmed PR according to RECIST Version 1.1 as assessed by investigator. Definition of BOR is specified in Section 5.2.5.1. The primary analysis population for confirmed ORR is RES.

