Missing		4	1	4	1	4	1	1

1 = Impute the date of the first dose; 2 = Impute the first of the month; 3 = Impute January 1 of the year; 4 = Impute January 1 of the stop year

The imputed dates will be used to determine whether an AE is/is not treatment emergent. Listings of AEs and concomitant medications will present the actual partial dates; imputed dates will not be shown.

Subjects who do not satisfy the criteria to be counted as responders or have insufficient data to determine or confirm a response per the RECIST guidelines (Version 1.1) will be considered as non-responders in the final analysis of response rates. No imputation of data will be done to determine individual subject response.

For continuous variables (e.g., clinical laboratory measurement, vital signs), subjects with missing baseline variable will be excluded from the analysis of change from baseline.

For all analyses other than pharmacokinetic analysis, all values will be included in the analyses. For analysis of pharmacokinetic data, only samples for which the time of sampling relative to the dose administration and the exact dose is known will be included.

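### The confirmed-PR rule omits the condition that confirmation comes at the next assessment, so PR, then SD, then PR again counts as a confirmed response, against the plan's own definition

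*SAP*

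**What the plan says.** SAP 5.1 builds the primary endpoint on best overall response (BOR): "Confirmed ORR is defined as the proportion of subjects whose best overall response (BOR) is a confirmed CR or confirmed PR". SAP 6.7 uses the same confirmed responses for the interim and final BOP2 counts.

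SAP 5.2.5.1 opens with a general sentence: "Confirmation of CR or PR should occur at the subsequent assessment no less than 4 weeks following the initial assessment". It then gives derivation bullets. The one for PR reads "If a subject has PR and another CR/PR at least 28 days apart, then the BOR for this subject is confirmed PR". Protocol 9.4.3.1 has the matching bullet, "If a subject has PR and another CR/PR more than 28 days apart, then the BOR for this subject is confirmed PR", with no opening sentence above it.

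Three other places bear on the point:

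- Protocol 4.1: "Response (CR or PR) must be confirmed with a repeat imaging scan 4 weeks (28 days + 7-day window) after first response".
- Protocol Appendix 12.9, Table 3 ("Best overall response when confirmation of CR and PR required"), gives a PR followed by SD a best response of SD.
- SAP 5.2.5.1 limits which records count: "Responses recorded after new anticancer therapy or PD will be excluded from BOR derivation". SD is not on that list.

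**The concern.** The opening sentence ties confirmation to the next assessment. The bullet, which is what gets programmed, asks only for a PR and one other CR or PR a minimum time apart. It is silent on adjacency and on SD in between. A subject whose PR was followed by SD at the confirmatory scan, and who later shows PR again, therefore meets the bullet although the first PR was not confirmed in the sense of Protocol 4.1. The length of the confirmation window is not at issue.

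Three results depend on the reading: the primary ORR, the responder counts compared with the BOP2 boundaries, and duration of response (DOR). SAP 5.2.1 starts DOR at the first CR or PR that is later confirmed. If the bullet is taken to confirm the first PR, the clock starts at a response that the next scan did not support. Subjects whose shrinkage sits close to 30% are the likely ones, because measurement variation can move them between PR and SD.

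**Working it through.** **Step 1: apply both rules to the same records.** Days follow the cohort 1 to 8 schedule: first scan at day 56, confirmatory scan 28 days later at day 84, next scheduled scan at day 112. SD needs a qualifying record at day 49 or later.

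| Record | Bullet as written | Confirmation at next assessment, at least 28 days later |
|---|---|---|
| PR d56, PR d84, SD d112 | confirmed PR | confirmed PR |
| PR d56, SD d84, SD d112 | SD | SD |
| PR d56, PD d84, PR d112 | SD | SD |
| PR d56, SD d84, PR d112 | **confirmed PR** | **SD** |
| PR d56, SD d84, SD d112, PR d168 | **confirmed PR** | **SD** |
| PR d56, SD d84, CR d112 | **confirmed PR** | **SD** |
| PR d56, SD d84, PR d112, PR d140 | confirmed PR | confirmed PR |

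The rules differ only where a response returns after SD and is not itself confirmed. In the last row BOR agrees, but DOR can start at day 56 or day 112: 112 − 56 = 56 days, or 56 / 30.4375 = 1.84 months.

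**Step 2: reproduce the plan's design figures.** With X1 responders among the first 20 and X2 among the next 20, the chance of claiming activity at true rate p is

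P(claim) = Σ over x ≥ r1 of P(X1 = x) × P(X2 ≥ r − x).

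Inputs from SAP 6.7, Table 3: (r1, r) = (4, 12) for cohort 1, (3, 10) for cohorts 2 and 4, (2, 7) for cohorts 3, 5, 7 and 8, (5, 14) for cohort 9. Recomputing the boundaries from the Beta(p0, 1 − p0) prior and the stated λ gives the same numbers for every cohort. Cohort 9 power at 45% is 0.918, which agrees with the stated 92%, and its type I error at 20% is 0.0187.

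**Step 3: slack in the type I error.** For (2, 7) at p = 0.10, the terms for x = 2, 3, 4, 5, 6 and 7 or more are

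0.0123 + 0.0253 + 0.0290 + 0.0194 + 0.0078 + 0.0024 = 0.0962.

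The limit is 0.10. If the interim rule is treated as non-binding, the single-stage value for 7 of 40 is 0.0995.

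**Step 4: illustration.** The documents give no frequency for PR-SD-PR records, so the added null ORR is an assumption.

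| Cohorts | Limit | No addition | +0.5 point | +1 point |
|---|---|---|---|---|
| 3, 5, 7, 8 | 0.10 | 0.096 | 0.117 | 0.140 |
| 1 | 0.10 | 0.085 | 0.099 | 0.114 |
| 2, 4 | 0.10 | 0.066 | 0.079 | 0.093 |
| 9 | 0.025 | 0.019 | 0.023 | 0.028 |

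**Step 5: weight of one subject.** In cohort 9, 14/40 (35.0%, 95% CI 20.6 to 51.7) meets the boundary. With one subject reclassified, 13/40 (32.5%, 95% CI 18.6 to 49.1) does not.

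**The case against.** The strongest reply is that the bullets do not stand alone. SAP 5.2.5.1 derives BOR according to RECIST 1.1, its opening sentence names the subsequent assessment, and SAP 6.9.2 says that subjects who "have insufficient data to determine or confirm a response per the RECIST guidelines (Version 1.1) will be considered as non-responders in the final analysis". On that view a programmer would never count PR-SD-PR.

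Part of this stands: the plan contains a stricter rule, so the fault is an unresolved conflict and not a settled decision to accept such records. It does not remove the conflict. The SAP introduces the bullets as the criteria by which BOR will be derived, and the protocol bullet has no opening sentence to restrain it. The rule in SAP 6.9.2 catches subjects who fail the responder criteria or lack data; a PR-SD-PR subject has the data and meets the bullet. The ORR regardless of confirmation in SAP 6.4.1.1 is looser still, so it cannot isolate these subjects.

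Table 3 compares a first with a subsequent time point and does not address a PR that recurs at a third scan. It shows that the first PR was not confirmed. That the final BOR is SD follows from the opening sentence and Protocol 4.1.

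Two wider readings are tempting and not supported:

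- A reader might infer that failed confirmations in general still count. They do not: PR-SD-SD gives SD under either rule, and responses after progression or new therapy are excluded.
- A reader might extend the point to CR followed by PR, or to two CRs with something else between them. Footnote a of Table 3 largely settles these. Disease seen after a true CR is PD, and later responses then drop out. If the first CR was really a PR, it is recoded and the best response is PR, which is what the bullet returns.

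**Conclusion.** The point holds in a narrow form. In both documents the confirmed-PR bullet is looser than the plan's own definition of confirmation. Applied literally, it turns PR-SD-PR, before progression or new therapy, into a confirmed response for the primary endpoint and the decision counts, and it can start DOR at an unconfirmed PR.

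The number of such subjects cannot be derived from the documents. A reader might infer from the table in step 4 that type I error is inflated; that is not established. Cohorts 2 and 4 stay within 0.10 even with one added point, and cohorts 1 and 9 stay within their limits with half a point. The illustration also assumes that the reference rates rest on consecutive confirmation, which the documents do not state. The boundaries inform a sponsor decision that also weighs safety and other activity data. What can be said is that cohorts 3, 5, 7 and 8 have almost no slack, and that one subject can decide a cohort at its boundary. The rule should be settled before further cohorts are read out.

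**What to change.** In SAP 5.2.5.1 and Protocol 9.4.3.1, replace the confirmed-PR bullet with one rule:

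- Confirmed PR is a PR followed, at the next evaluable assessment at least 28 days later, by PR or CR.
- Intervening NE assessments are allowed; intervening SD is not.
- A PR that recurs after SD needs its own confirmation, and DOR then starts at that PR.
- CR followed by PR is handled by footnote a of Table 3 in Protocol Appendix 12.9.

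Using the same wording in both places also removes the difference between more than 28 days (protocol) and at least 28 days (SAP), which matters for a scan on exactly day 28.

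List the subjects who qualify only under the looser bullet, and report ORR including them as a sensitivity analysis. Do this also for cohorts already analysed. For cohort 5, Protocol 2.4.1 reports 1 CR and 10 PR among 46 subjects (11/46 = 23.9%) against a minimum of 7 responders set for 40. A listing would show whether any of these depend on the looser rule without reopening the readout.

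The cost is wording in two documents and a small programming change. ORR may fall slightly. Sample size and boundaries are unchanged.
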